### 1849 *6.2.4 Additional Secondary Analyses*

1850 Both ICU and hospital length of stay will be compared using Wilcoxon Rank Sum tests. Ventilator  
1851 and shock free days over the first 7-days after enrollment will likewise be compared using the

1852 Wilcoxon Rank Sum given that the data will likely be not normally distributed. In these latter two  
1853 analyses, patients who expire prior to 7-days will be assessed to have 0 ventilator or shock free  
1854 days if they had died while on a ventilator or vasopressor respectively. The incidence of delirium will  
1855 be compared using the Fisher's exact test. For the quality-of-life outcome (i.e. 90-day SF-36), the  
1856 primary analysis will only include patients with available data. As a secondary analysis, multiple  
1857 imputation will be used to estimate SF-36 scores in all patients not known to be dead at 90 -days.  
1858

#### 1859 *6.2.5 Subgroup analyses*

1860 The analysis will include three pre-defined subgroup analyses for the primary and key secondary  
1861 outcomes according to 1) participants with initially high SOFA scores ( $\geq 9$ ). This cut-off was chosen  
1862 to represent a population with a  $\geq 50\%$  predicted likelihood of mortality 2) baseline vitamin B1  
1863 deficiency and 3) baseline adrenal insufficiency. We will not plan to perform a subgroup analysis  
1864 according to vitamin C deficiency, as prior work has shown that the vast majority of participants with  
1865 septic shock have vitamin C levels below the reference range. Vitamin B1 deficiency will be  
1866 defined as a plasma vitamin B1 level  $\leq 7$  nmol/L as has been previously described. Adrenal  
1867 insufficiency will be defined as a cortisol level  $< 10\mu\text{g/dL}$ . The trial is not powered to detect  
1868 subgroup differences and these will be considered exploratory and hypothesis generating.  
1869

#### 1870 *6.2.6 Statistical stopping criteria*

1871 Since the primary outcome is not mortality, there will be no formal stopping criteria for efficacy.  
1872 There will be no predefined stopping criteria for futility since enrollment of the full cohort might allow  
1873 for detection of efficacy in subgroups or in other outcomes even if the primary outcome is negative.  
1874

## 1875 **7. DATA COLLECTION AND MANAGEMENT**

### 1876 **7.1 Data collection process**

1877 Data collection will be the responsibility of the individual site investigators with oversight from the trial  
1878 coordinating center. Most variables (i.e. demographics, sepsis characteristics and laboratory  
1879 results) will be obtained prospectively from the electronic medical record. 30-day follow-up  
1880 regarding safety and mortality end-points will be obtained via telephone call post-discharge (unless  
1881 the participant remains in the hospital at 30-days). Data will be entered directly into the online  
1882 database software (see below).  
1883

### 1884 **7.2 Variables**

1885 Will be provided on the online CRF. A PDF version is available upon request.  
1886

### 1887 **7.3 Data quality and validity**

1888 Data quality and validity will be optimized by using a detailed data dictionary which will be  
1889 distributed to all sites. Data quality will be monitored both centrally by the coordinating site and  
1890 locally by each site principal investigator.  
1891

### 1892 **7.4 Data storage and security**

1893 The database application we will use is REDCap Cloud (<https://www.redcapcloud.com/>). REDCap  
1894 Cloud is a professional database that provides a user-friendly interface. The REDCap Cloud data  
1895 management system is secure, fully compliant with all regulatory guidelines, and includes a  
1896 complete audit-trail for data entry validation. Through these mechanisms, as well as relevant  
1897 training for all involved parties, participant confidentiality will be safeguarded. All members of the  
1898 research team will be required to complete standardized training in REDCap cloud, which will be  
1899 documented within the software.  
1900

1901 The consent form and other trial documents for each participant will initially be stored in a secure,  
1902 locked place at the individual sites. Participating sites will be responsible for maintaining their own  
1903 trial documents and study materials (e.g. signed ICFs, site logs etc). Trial documents generated at  
1904 the Coordinating Center will be maintained the Coordinating Center. Following completion of the

1905 trial, documents will be maintained for a period of at least 2-years at each site per FDA regulations  
1906 (or longer depending on local IRB guidelines).  
1907

## 1908 **8. ETHICAL CONSIDERATIONS**

### 1909 **8.1 Risks and Benefits**

#### 1910 *8.1.1 Potential benefits*

1911 **Potential Benefits to Individual Participant:** Assuming our hypothesis is correct and our results are  
1912 comparable to those previously published, individual participants enrolled in our study and  
1913 randomized to the treatment arm will benefit from a better trajectory of organ failure and improved  
1914 mortality. As many participants who survive an initial episode of sepsis will have a future admission for  
1915 sepsis, participants participating in this study but randomized to the placebo arm may see a future  
1916 benefit from knowledge gained.  
1917

1918 **Potential Benefits to Society:** Septic shock remains a highly morbid clinical condition for which there  
1919 is no specific therapy. Our study, assuming our hypothesis is confirmed, will provide strong support for  
1920 the widespread adoption of vitamin C, corticosteroids, and vitamin B1 for participants with septic  
1921 shock. This, in turn, will significantly improve participant outcomes and reduce the global burden of  
1922 death related to septic shock. Thus, even if participants are randomized to the placebo arm, their  
1923 involvement with this study has tremendous potential benefits for society as whole. If vitamin C,  
1924 corticosteroids, and vitamin B1 are found to be neutral or harmful (the latter being highly unlikely),  
1925 society will benefit as the study will likely prevent the widespread dissemination of an ineffective  
1926 medication combination.  
1927

#### 1928 *8.1.2 Potential harms*

##### 1929 **Study Drug**

1930 Vitamin C – Ascorbic acid is a water-soluble essential vitamin that is safe even at high doses.  
1931 Nevertheless, adverse effects related to high-dose ascorbic acid have been described. These  
1932 adverse effects include diarrhea/abdominal bloating, increased oxalate excretion, iron overload in  
1933 participants with hemochromatosis, and hemolysis in participants with G6PD deficiency. We  
1934 exclude participants with known renal failure (CKD  $\geq 3b$ ), known G6PD deficiency, or known  
1935 hemochromatosis to limit these potential risks. We will additionally exclude participants with known  
1936 allergy to ascorbic acid. Ascorbic acid has additionally been used in at least 3 clinical trials in critically-  
1937 ill populations without major associated adverse effect.  
1938

1939 Hydrocortisone – Hydrocortisone is a well-established medication for the treatment of refractory  
1940 shock in sepsis. Some studies (e.g. CORTICUS) have found an increased incidence of secondary  
1941 infection in participants with septic shock who receive steroids. This finding has not been  
1942 replicated in other large trials of corticosteroids for sepsis. Additional hypothetical risks to the  
1943 administration of hydrocortisone to participants with septic shock (e.g. increased gastro-intestinal  
1944 bleeding, muscle weakness, and delirium) have not been found in clinical trials of corticosteroids in  
1945 sepsis. Finally, hydrocortisone may increase the risk of hyperglycemia and hyponatremia.  
1946

1947 Hydrocortisone will not be tapered in this study as prior studies have shown benefit with  
1948 corticosteroids in septic shock without a taper. In addition, a recent large trial of corticosteroids in  
1949 septic shock (ADRENAL, NEJM 2018) randomized patients to 7-days of corticosteroids or placebo  
1950 and did not include a taper. In that trial there was no reported difference in rates of recurrent shock.  
1951

1952 Vitamin B1 – The only potential serious side effect that has been reported from vitamin B1  
1953 administration is an extremely rare anaphylactic reaction (1:250,000 cases) and this might not even  
1954 be of issue with the current manufactured version of vitamin B1 in the United States. The risk of an  
1955 anaphylactic reaction was associated with a vitamin complex dispensed in Europe, and whether

1956 vitamin B1 was the actual offending agent remains unknown; however, this 0.0004% theoretical  
1957 chance of an adverse reaction is incredibly low. In a series of 989 participants in the United States  
1958 who received intravenous vitamin B1, none had an anaphylactic reaction and the only reported side  
1959 effects were minor consisting of transient local irritation or in one case pruritus (0.093%). Further  
1960 safety data comes from the clinical use of intravenous vitamin B1 at our coordinating site. At Beth  
1961 Israel Deaconess Medical Center (BIDMC, coordinating center) vitamin B1 is provided liberally for  
1962 participants with nutritional deficiency – for example, BIDMC has administered intravenous vitamin  
1963 B1 in over 8,000 separate participant encounters from 2002 until present. Despite this heavy usage,  
1964 no adverse reactions were reported in any of the 8,000 participant encounters.

1965  
1966 The combination of vitamin C, hydrocortisone and vitamin B1 – To date, the only study of the  
1967 combination of vitamin C, hydrocortisone and vitamin B1 was the above referenced study by Marik  
1968 et. al.

1969  
1970 All procedures will take place at the study site. All research procedures and monitoring will be  
1971 conducted by experienced personnel, and participants will be in the ICU given critical illness. This  
1972 permits closer observation and more detailed monitoring by clinicians familiar with the care of  
1973 participants experiencing and resuscitated from septic shock.

#### 1974 1975 **Blood Collection**

1976 Most participants will have existing venous or arterial catheters in place and we will be able to collect  
1977 blood from these ports, essentially eliminating the risks associated with blood collection. In the very  
1978 rare case that a participant does not have an indwelling line, the risk of venipuncture is extremely  
1979 low, and will not exceed the risk of clinical blood draws the participant will already be receiving.

#### 1980 1981 **Loss of Confidentiality**

1982 All measures will be taken to ensure that no confidential information is released. All participant  
1983 information will be stored in a password protected database to which only study investigators will  
1984 have access. Additionally, all hard copies of study data will be kept in a locked office accessible only  
1985 to study investigators. Thus, the risk of loss of confidentiality is very low.

### 1986 1987 **9. MONITORING**

#### 1988 **9.1 Institutional Review Board (IRB)**

1989 The study will be reviewed and approved by the IRB at each participating site.

#### 1990 1991 **9.2 Data Safety and Monitoring Board (DSMB)**

1992 The DSMB will be responsible for safeguarding the interests of trial participants, assessing the  
1993 safety and efficacy of the interventions during the trial, and for monitoring the overall conduct of the  
1994 clinical trial. The DSMB will consist of three clinicians with critical care experience in the  
1995 management of septic participants. An independent biostatistician/epidemiologist will prepare all  
1996 DSMB reports. The DSMB members will be chosen such to avoid any financial or intellectual  
1997 conflicts of interest. The DSMB will review deidentified data after every 50 participants are enrolled  
1998 to assess for safety; unless there are group differences necessitating unblinding (as determined by  
1999 the DSMB), the DSMB will be blinded to treatment groups. The trial will continue while the DSMB  
2000 review data. After each review, the DSMB will create a short report to the steering committee with  
2001 recommendations for continuation, modifications, or termination of the trial. Criteria for  
2002 recommending termination will be at the discretion of the DSMB and there will be no formal  
2003 statistical criteria for termination due to efficacy or safety. A detailed charter for the DSMB will be  
2004 provided.

[figure not shown]

## 11. TIMELINE AND ENROLLMENT

### 11.1 Timeline

2048  
2049  
2050  
2051  
2052  
2053  
2054  
2055

### 11.2 Screening & Enrollment

Enrollment at each site will be continuously monitored by the site investigator and the principal investigator. Each site will be expected to maintain a screening log including all participants who meet all eligibility criteria at that site. A standardized screening log will be provided to each site via RedCap Cloud—thus allowing for continuous updating of the screening log and will allow capture of all screening failures.

2056 Enrollment will be competitive (i.e. without specific enrollment caps). Number of enrollments at each  
2057 site will be shared with all sites on a monthly basis. Sites will be expected to complete all elements  
2058 of the online CRF within 48-hours of each time point. In the case that a site continuously  
2059 underperforms despite troubleshooting and feedback, the steering committee will evaluate whether  
2060 enrollment will continue at that site.  
2061

## 2062 **12. FUNDING**

2063 Funding for the present trial is provided by the Good Ventures Foundation  
2064 (<http://www.goodventures.org/>). The funding agency will have no role in the design and conduct of  
2065 the study, collection, management, analysis, and interpretation of the data, preparation, review, or  
2066 approval of the manuscript, or the decision to submit the manuscript for publication.  
2067

## 2068 **13. PUBLICATION**

2069 The manuscript will adhere to the CONSORT guidelines. The principal investigator will be  
2070 responsible for assigning authorship position and will follow authorship guidelines from the  
2071 International Committee of Medical Journal Editors. At a minimum, all members of the Steering  
2072 Committee and all site Principal Investigators (for sites enrolling at least 10 participants) will be  
2073 included in the primary author list. The main results will be presented at an international conference.  
2074 The trial results will be shared with participating sites and via press releases but not directly with the  
2075 participants.  
2076

## 2077 **14. DATA SHARING**

2078 Six months after the publication of the last results, all de-identified individual participant data will be  
2079 made available for data sharing. Procedures, including re-coding of key variables, will be put in  
2080 place to allow for complete de-identification of the data. All relevant trial-related documents,  
2081 including the protocol, data dictionary, and the main statistical code, will be shared along with the  
2082 data. There will be no predetermined end date for the data sharing. Data will be available for any  
2083 research purpose to all interested parties who have approval from an independent ethics review  
2084 committee and who have a methodological sound proposal as determined by the steering  
2085 committee of the current trial. Interested parties will be able to request the data by contacting the  
2086 principal investigator. Authorship of publications emerging from the shared data will follow standard  
2087 authorship guidelines from the International Committee of Medical Journal Editors and might or  
2088 might not include authors from the steering committee depending on the nature of their involvement.  
2089

## 2090 **15. TASKS AND RESPONSIBILITIES**

2091 Principal investigator and sponsor: Overall responsibility for protocol development, funding, budget  
2092 overview, data dictionary development, ethical approval, trial registration, daily management, trial  
2093 oversight and collection of adverse events, contact to the pharmacy, contact to Good Clinical  
2094 Practice monitoring unit and the data and safety monitoring board, assessment of overall  
2095 recruitments, potential recruitment of additional sites, data analysis, and dissemination and  
2096 presentation of results.  
2097

2098 Steering committee: Protocol development, funding, budget overview, data dictionary development,  
2099 trial oversight, dissemination of results, responsibilities as principal investigator for short time  
2100 periods.  
2101

2102 Site investigators: Responsible for site-specific enrollment, evaluation of eligible patients not  
2103 included, education of personnel at participating sites, reporting of site-specific issues or challenges  
2104 to the principal investigator, participant consent for data collection, collecting and reporting data  
2105 regarding adverse drug events.  
2106

2107 Clinical team: Administration of the study drug, participant consent for data collection.

2108  
2109  
2110  
2111  
2112  
2113  
2114  
2115  
2116  
2117  
2118  
2119  
2120  
2121  
2122  
2123  
2124  
2125  
2126  
2127  
2128  
2129  
2130  
2131  
2132  
2133  
2134  
2135  
2136  
2137  
2138  
2139  
2140  
2141  
2142  
2143  
2144  
2145  
2146  
2147  
2148  
2149  
2150  
2151  
2152  
2153  
2154  
2155  
2156  
2157

- 2304 79. Levine M, Rumsey SC, Daruwala R, Park JB, Wang Y. Criteria and recommendations for vitamin C  
2305 intake. *Jama*. 1999;281(15):1415-1423.
- 2306 80. Annane D, Sebille V, Charpentier C, et al. Effect of treatment with low doses of hydrocortisone and  
2307 fludrocortisone on mortality in patients with septic shock. *Jama*. 2002;288(7):862-871.
- 2308 81. Wrenn KD, Murphy F, Slovis CM. A toxicity study of parenteral thiamine hydrochloride. *Annals of*  
2309 *emergency medicine*. 1989;18(8):867-870.
- 2310 82. International Committee of Medical Journal Editors. Defining the Role of Authors and Contributors.  
2311 2017; [http://www.icmje.org/recommendations/browse/roles-and-responsibilities/defining-the-role-](http://www.icmje.org/recommendations/browse/roles-and-responsibilities/defining-the-role-of-authors-and-contributors.html)  
2312 [of-authors-and-contributors.html](http://www.icmje.org/recommendations/browse/roles-and-responsibilities/defining-the-role-of-authors-and-contributors.html). Accessed July 6, 2017.
- 2313 83. Taichman DB, Sahni P, Pinborg A, et al. Data Sharing Statements for Clinical Trials - A Requirement of  
2314 the International Committee of Medical Journal Editors. *N Engl J Med*. 2017;376(23):2277-2279.

2315 **Appendices**

2316

2317 **Appendix 1: Abbreviations**

- 2318 ICH.....International Conference on Harmonization
- 2319 SPIRIT.....Standard Protocol Items: Recommendations for Interventional Trials
- 2320 ACT.....Ascorbic Acid, Corticosteroids, and Thiamine
- 2321 CKD.....Chronic Kidney Disease
- 2322 SOFA.....Sequential Organ Failure Assessment
- 2323 IND.....Investigational New Drug
- 2324 FDA.....Food and Drug Administration
- 2325 ICU.....Intensive Care Unit
- 2326 SaO2.....Oxygen Saturation
- 2327 FiO2.....Fraction of Inspired Oxygen
- 2328 GCS.....Glasgow Coma Scale
- 2329 UOP.....Urine Output
- 2330 RRT.....Renal Replacement Therapy
- 2331 CAM.....Confusion Assessment Method
- 2332 NCHS..... National Center for Health Statistics
- 2333 NDI.....National Death Index
- 2334 AKI.....Acute Kidney Injury
- 2335 SD..... standard deviation
- 2336 CRF.....Case Report Form
- 2337 BIDMC.....Beth Israel Deaconess Medical Center (Coordinating Center)
- 2338 IRB.....Institutional Review Board
- 2339 DSMB.....Data Safety and Monitoring Board

2340

2341

2342

2343

2344

2345

2346

2347

2348

2349

2350

2351

2352

2353

2354

2355

2356

2357

2358

2359

2360

2361

2362

### CAM-ICU Worksheet

Feature 1: Acute Onset or Fluctuating Course	Score	Check here if Present		

Is the pt different than his/her baseline mental status? OR Has the patient had any fluctuation in mental status in the past 24 hours as evidenced by fluctuation on a sedation scale (i.e., RASS), GCS, or previous delirium assessment?
	Either question Yes →			
Feature 2: Inattention				

Letters Attention Test (See training manual for alternate Pictures)
 
Directions: Say to the patient, "I am going to read you a series of 10 letters. Whenever you hear the letter 'A,' indicate by squeezing my hand." Read letters from the following letter list in a normal tone 3 seconds apart.
 
S A V E A H A A R T
 
Errors are counted when patient fails to squeeze on the letter "A" and when the patient squeezes on any letter other than "A."
			Number of Errors >2 →	
Feature 3: Altered Level of Consciousness				

Present if the Actual RASS score is anything other than alert and calm (zero)
	RASS anything other than zero →			
Feature 4: Disorganized Thinking				

Yes/No Questions (See training manual for alternate set of questions)
 
 
1. Will a stone float on water?
 
2. Are there fish in the sea?
 
3. Does one pound weigh more than two pounds?
 
4. Can you use a hammer to pound a nail?
 
 
Errors are counted when the patient incorrectly answers a question.
 
Command Say to patient: "Hold up this many fingers" (Hold 2 fingers in front of patient) "Now do the same thing with the other hand" (Do not repeat number of fingers) *If pt is unable to move both arms, for 2nd part of command ask patient to "Add one more finger"
 
An error is counted if patient is unable to complete the entire command.
			Combined number of errors >1 →	
Overall CAM-ICU				
Feature 1 plus 2 and either 3 or 4 present = CAM-ICU positive	Criteria Met →	 CAM-ICU Positive (Delirium Present)		
	Criteria Not Met →	 CAM-ICU Negative (No Delirium)		

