### 5. OUTCOMES

#### 5.1 Definitions

##### 5.1.1 Primary Outcome

The primary outcome will be the absolute change in the Sequential Organ Failure Assessment (SOFA) score from enrollment (time=0) to 72 hours after drug administration. The SOFA score will be defined using a modification in which the SaO2/FiO2 ratio is substituted for the PaO2/FiO2 ratio as has been previously described. This modified score will be used so that participants without an existing arterial catheter can be spared arterial puncture.

Points	SaO 2 */FiO 2 §	Blood Pressure	GCS 	Bilirubin (mg/dL)	Creatinine (mg/dL)	Platelets (x10  µL)
1	<400	< 70 mm/Hg	13–14	1.2–1.9	1.2 – 1.9	<150
2	<326	dopamine ≤ 5 µg/kg/min or dobutamine (any dose)	10–12	2–5.9	2.0 – 3.4	<100
3	<236 (and receiving invasive or non-invasive mechanical ventilation)	dopamine > 5µg/kg/min, epinephrine/norepinephrine ≤ 0.1 µg/kg/min	6–9	6–11.9	3.5 – 4.9 Or UOP † <500ml/day	<50
4	<151 (and receiving invasive or non-invasive mechanical ventilation)	dopamine > 15, epinephrine/norepinephrine > 0.1 µg/kg/min	<6	>12	> 5.0 UOP † <200ml/day Or receiving renal replacement therapy	<20

\*SaO2=Oxygen saturation (%); § = Fraction of inspired oxygen (%); || = Glasgow Coma Scale; † = Urine Output

FiO2 will be determined by using either the set FiO2 (for patients receiving invasive or non-invasive mechanical ventilation) or by adding 3% FiO2 for each liter/minute of supplemental oxygen added up to 100% FiO2 (for patients not receiving mechanical ventilation). Patients with an SaO2/FiO2 ratio <236 who are not receiving invasive or non-invasive mechanical ventilation, will be assigned a score of 2.

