## 5.3 Additional Secondary Outcomes

### 5.3.1 Additional secondary outcomes

Additional secondary outcomes will include length of ICU stay, length of hospital stay, ventilator-free days over the first 7-days after enrollment, shock-free days over the first 7-days after enrollment,

and the incidence of delirium on day #3 of the ICU stay (as assessed using the Confusion Assessment Method [CAM-ICU] system). Sites at which the CAM-ICU is performed daily as part of standard-of-care should assess whether delirium occurs on any day during the initial ICU stay. See Appendix #2.

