### 6.2.4 Additional Secondary Analyses

Both ICU and hospital length of stay will be compared using Wilcoxon Rank Sum tests. Ventilator and shock free days over the first 7-days after enrollment will likewise be compared using the Wilcoxon Rank Sum given that the data will likely be not normally distributed. In these latter two analyses, patients who expire prior to 7-days will be assessed to have 0 ventilator or shock free days if they had died while on a ventilator or vasopressor respectively. The incidence of delirium will be compared using the Fisher's exact test. For the quality-of-life outcome (i.e. 90-day SF-36), the primary analysis will only include patients with available data. As a secondary analysis, multiple imputation will be used to estimate SF-36 scores in all patients not known to be dead at 90 -days.

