#### *8.1.2 Potential harms*

##### **Study Drug**

Vitamin C – Ascorbic acid is a water-soluble essential vitamin that is safe even at high doses. Nevertheless, adverse effects related to high-dose ascorbic acid have been described. These adverse effects include diarrhea/abdominal bloating, increased oxalate excretion, iron overload in participants with hemochromatosis, and hemolysis in participants with G6PD deficiency. We exclude participants with known renal failure, known G6PD deficiency, or known hemochromatosis to limit these potential risks. We will additionally exclude participants with known allergy to ascorbic

acid. Ascorbic acid has additionally been used in at least 3 clinical trials in critically-ill populations without major associated adverse effect.

Hydrocortisone – Hydrocortisone is a well-established medication for the treatment of refractory shock in sepsis. Some studies (e.g. CORTICUS) have found an increased incidence of secondary infection in participants with septic shock who receive steroids. This finding has not been replicated in other large trials of corticosteroids for sepsis. Additional hypothetical risks to the administration of hydrocortisone to participants with septic shock (e.g. increased gastro-intestinal bleeding, muscle weakness, and delirium) have not been found in clinical trials of corticosteroids in sepsis. Finally, hydrocortisone may increase the risk of hyperglycemia and hyponatremia.

Hydrocortisone will not be tapered in this study as prior studies have shown benefit with corticosteroids in septic shock without a taper. In addition, a recent large trial of corticosteroids in septic shock (ADRENAL, NEJM 2018) randomized patients to 7-days of corticosteroids or placebo and did not include a taper. In that trial there was no reported difference in rates of recurrent shock.

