Appendix 2: CAM-ICU Form

### CAM-ICU Worksheet

Feature 1: Acute Onset or Fluctuating Course	Score	Check here if Present		

Is the pt different than his/her baseline mental status?
 
OR
 
Has the patient had any fluctuation in mental status in the past 24 hours as evidenced by fluctuation on a sedation scale (i.e., RASS), GCS, or previous delirium assessment?
	Either question Yes →			
Feature 2: Inattention				

Letters Attention Test (See training manual for alternate Pictures)
 
Directions: Say to the patient, "I am going to read you a series of 10 letters. Whenever you hear the letter 'A,' indicate by squeezing my hand." Read letters from the following letter list in a normal tone 3 seconds apart.
 
S A V E A H A A R T
 
Errors are counted when patient fails to squeeze on the letter "A" and when the patient squeezes on any letter other than "A."
			Number of Errors >2 →	
Feature 3: Altered Level of Consciousness				

Present if the Actual RASS score is anything other than alert and calm (zero)
	RASS anything other than zero →			
Feature 4: Disorganized Thinking				

Yes/No Questions (See training manual for alternate set of questions)
 
 
1. Will a stone float on water?
 
2. Are there fish in the sea?
 
3. Does one pound weigh more than two pounds?
 
4. Can you use a hammer to pound a nail?
 
 
Errors are counted when the patient incorrectly answers a question.
 
Command                      Say to patient: "Hold up this many fingers" (Hold 2 fingers in front of patient) "Now do the same thing with the other hand" (Do not repeat number of fingers) *If pt is unable to move both arms, for 2nd part of command ask patient to "Add one more finger"
 
An error is counted if patient is unable to complete the entire command.
			Combined number of errors >1 →	
Overall CAM-ICU				
Feature 1 plus 2 and either 3 or 4 present = CAM-ICU positive	Criteria Met →	 CAM-ICU Positive (Delirium Present)		
	Criteria Not Met →	 CAM-ICU Negative (No Delirium)		

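### Delirium is called incidence but pools new cases with delirium that predates the first dose, and its unadjusted Fisher test leaves the enrollment GCS unused

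*SAP*

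**What the plan says.** Protocol 5.3.1 lists among the additional secondary outcomes "the incidence of delirium on day #3 of the ICU stay", assessed by CAM-ICU. Sites that already perform CAM-ICU daily "should assess whether delirium occurs on any day during the initial ICU stay". Neither window is limited to time after enrollment, and no CAM-ICU is required at enrollment.

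Section 6.2.4 reads "The incidence of delirium will be compared using the" Fisher's exact test. No covariate or stratum is named.

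The worksheet (Protocol Appendix 2, with the same wording in both copies in the SAP file) meets Feature 1 if either of two questions is answered yes: "Is the pt different than his/her baseline mental status", or "Has the patient had any fluctuation in mental status in the past 24 hours". A positive result also needs Feature 2 (inattention) and either Feature 3 or Feature 4.

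Two other places bear on the point. Section 5.1.2 limits renal failure to events arising after study enrollment. Section 5.1.1 defines the primary outcome as the "absolute change in the Sequential Organ Failure Assessment (SOFA) score from enrollment (time=0) to 72 hours", and GCS is one of the six SOFA components, so a GCS is needed at enrollment.

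**The concern.** Incidence means new cases, but the definition records whether delirium is present. Septic shock can disturb mental state before any study drug is given, and nothing in 5.3.1 or 6.2.4 separates delirium that was already there. At daily-testing sites, ICU days before the first dose can fall inside the window, since 4.3 allows consent up to 24 hours after vasopressors start. The contrast with the renal definition suggests an oversight rather than a choice.

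Persistent earlier delirium contributes equally to both arms, so it shrinks the observed difference and makes the result hard to read as drug-related new delirium. A pre-treatment measure related to mental state is also available and unused. At stake is the sensitivity and interpretation of one additional secondary outcome, not the primary result.

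**Working it through.** **No plan figure to reproduce.** Section 6.1 gives power only for the primary and key secondary outcomes. As a check of the method, exact enumeration of the two-sided Fisher test was applied to the two Fisher-based figures there:
- renal failure 30% v 55%, 100 per arm: 93.9% (plan 94%);
- mortality 20% v 40%, 91 per arm: 80.8% (plan 80% with 182).

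**Step 1: dilution.** Assume new delirium of 40% on placebo and 20% on treatment, and a share π already delirious and still positive in both arms. Observed rate = π + (1 − π) × new rate. With π = 0.30:
- placebo 0.30 + 0.70 × 0.40 = 0.58; treatment 0.30 + 0.70 × 0.20 = 0.44;
- the risk difference falls from 20 to 14 points, and the risk ratio moves from 0.50 to 0.44/0.58 = 0.76;
- Fisher power at 100 per arm falls from 84% to 47%.

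**Step 2: what GCS stratification recovers.** Inputs from the documents: 100 per arm, two-sided 0.05. Assumed: the share with enrollment GCS below 15, placebo delirium in each GCS stratum, and a treatment odds ratio (OR) of 0.5. On the odds scale, treated odds = 0.5 × placebo odds. For example, 60% gives odds 1.5, then 0.75, so 42.9%; 20% gives 0.25, then 0.125, so 11.1%. With half in each stratum, the totals are 40% v 27%.

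The Mantel-Haenszel (MH) statistic, without continuity correction, is [Σ(aₖ − n₁ₖmₖ/Nₖ)]² / Σ[n₁ₖn₀ₖmₖ(Nₖ − mₖ)/(Nₖ²(Nₖ − 1))], referred to 3.84. Here aₖ is treated cases, mₖ all cases, and n₁ₖ, n₀ₖ, Nₖ the arm and total sizes in stratum k. Power in %, 200,000 simulated trials per cell:

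| Share GCS <15; placebo delirium (<15 / 15) | Effect | Fisher | Chi-square | MH | MH − chi-square |
|---|---|---|---|---|---|
| 50%; 60/20 | OR 0.5 in both strata | 43.5 | 49.9 | 55.9 | 6.0 |
| 40%; 70/15 | both | 30.7 | 36.6 | 47.6 | 11.0 |
| 60%; 80/20 | both | 33.8 | 39.2 | 51.0 | 11.8 |
| 50%; 50/30 (weak marker) | both | 53.1 | 59.5 | 60.6 | 1.1 |
| 50%; 60/20 | GCS 15 only | 7.4 | 9.8 | 11.1 | 1.3 |
| 40%; 70/15 | GCS 15 only | 6.8 | 9.3 | 11.8 | 2.5 |
| 60%; 80/20 | GCS 15 only | 6.5 | 8.7 | 9.9 | 1.2 |
| 50%; 50/30 (weak marker) | GCS 15 only | 11.4 | 14.6 | 15.3 | 0.7 |

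With no effect in either stratum, Fisher rejects in 3.5–3.8% of trials, chi-square in 5.0–5.4% and MH in 5.0%. Part of the gap between Fisher and MH is therefore Fisher's conservatism; the last column isolates the stratification.

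**Step 3: GCS as an imperfect marker.** Return to the Step 1 model and stratify on a marker with assumed 75% sensitivity and specificity for enrollment delirium. MH power rises from 75.8% to 76.6% at π = 10%, from 53.4% to 55.2% at 30%, and from 30.5% to 35.4% at 50%. Stratifying on true enrollment delirium would give 84.1%, 73.4% and 58.7%.

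**The case against.** The strongest reply is that delirium status on a fixed day is a legitimate randomized outcome. Delirium present at enrollment that clears by day 3 could be a treatment benefit, so those participants are informative. Randomization keeps the unadjusted test valid. The plan is consistently unadjusted and claims no power for this outcome. GCS is not a delirium instrument, and the documents do not say how it is scored under sedation. The larger gains need both a strong prognostic gap and an effect in participants whose GCS is already low; without either, the gain is small.

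All of that stands, and it limits the size of the point. It does not defend the incidence label or the missing after-enrollment limit, and it gives no reason to leave a valid pre-treatment stratifier unused.

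A reader might also infer four stronger things that the documents do not support:
- **That the form counts any departure from the pre-illness state as delirium.** Feature 1 alone is not enough, and pre-illness does not appear in the text. The patient's usual state is a natural reading of the undefined baseline. If a site read it as enrollment, an unchanged participant would meet Feature 1 only through 24-hour fluctuation. The form detects delirium on the day; the gap lies in 5.3.1 and 6.2.4.
- **That the Fisher test is biased or inflates false positives.** Its null rejection rate is below 5%.
- **That the protocol treats delirium as an established harm of hydrocortisone.** Section 8.1.2 lists it ("e.g. increased gastro-intestinal bleeding, muscle weakness, and delirium") as hypothetical and says such risks were not found in corticosteroid trials in sepsis.
- **That delirium predating the drug cannot be affected by it.** It may resolve faster or slower, and the larger gains above depend on an effect in the low-GCS stratum.

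**Conclusion.** The point holds as a minor improvement to definition and analysis. The outcome mixes persisting and new delirium under a label that promises only new cases, and a usable pre-treatment covariate is left out.

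The planned test is valid, so the cost is dilution, loss of power and unclear interpretation. Stratification adds roughly 0.5 to 2.5 points over chi-square when GCS is weakly prognostic or the effect is confined to GCS 15, and up to about 12 points when GCS is strongly prognostic and the odds ratio is 0.5 in both strata. In the worst case shown, power stays near 10% whichever test is used, so stratification does not cure dilution. Nor does it turn the outcome into new-onset delirium. Every delirium rate, the GCS distribution and the treatment effect are assumptions; the documents give none.

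**What to change.** - **6.2.4:** compare delirium with a Mantel-Haenszel test and a stratified risk difference with 95% CI, using enrollment GCS (15 v below 15) as the stratum. Keep Fisher's test as the unadjusted check.
- **5.3.1:** call the outcome delirium on the assessment day, and limit the any-day window at daily-testing sites to days after enrollment.
- **Reporting:** show the GCS 15 stratum descriptively, without presenting it as confirmed new-onset delirium.

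The cost is a few sentences and a few lines of code, with no new data. In the SOFA table the GCS component first scores a point at 13–14, so the split is recoverable even if only component points are stored. The downside is small: GCS is an imperfect proxy, especially in sedated participants, and the gain may be slight. Because it is measured before treatment, stratifying on it does not bias the comparison, and it lost no power in any scenario above.
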